The study investigator shall complete an Unanticipated Adverse Device Effect Form and submit to the sponsor and to the reviewing Institutional Review Board (IRB) a report of any unanticipated adverse device effect occurring during an investigation as soon as possible, but in no event later than 10 working days after the investigator first learns of the effect (21 CFR 812.150(a)(1)). A sponsor who conducts an evaluation of an unanticipated adverse device effect under 812.46(b) shall report the results of such evaluation to the FDA and to all reviewing IRB's and participating investigators within 10 working days after the sponsor first receives notice of the effect. Thereafter the sponsor shall submit such additional reports concerning the effect as FDA requests (21 CFR 812.150(b)(1)).

An unanticipated adverse device effect will be added to the subject informed consent form under IRB approval. No new subject will be enrolled in the study until after the change has been made to the consent form. Therefore, all subsequent potential subjects will be made aware of the unanticipated problem prior to deciding on study participation. Subjects who have already completed the study will not be informed about the occurrence of an unanticipated problem unless it is determined to have occurred after study completion.

Reporting Events to Subjects

An occurring AE or SAE not already captured as a potential risk of study participation in the subject informed consent document will be added to the consent form under IRB approval. No new subject will be enrolled in the study until after the change has been made to the consent form. Therefore, all subsequent potential subjects will be made aware of the new AE or SAE prior to deciding on participation.

Subjects who have already completed the study will not be informed about newly occurring AEs or SAEs unless the AE or SAE is determined to have occurred after study completion.

UNANTICIPATED PROBLEMS (UP)

Unanticipated Problems (UP) Definition

The Office for Human Research Protections (OHRP) considers unanticipated problems involving risks to subjects or others to include, in general, any incident, experience, or outcome that meets **each** of the following criteria:

- Unexpected in terms of nature, severity, or frequency given (a) the research procedures that are described in the protocol-related documents, such as the Institutional Review Board (IRB)-approved research protocol and informed consent document; and (b) the characteristics of the subject population being studied;
- Related or possibly related to participation in the research (“possibly related” means there is a reasonable possibility that the incident, experience, or outcome may have been caused by the procedures involved in the research); and
- Suggests that the research places subjects or others at a greater risk of harm (including physical, psychological, economic, or social harm) than was previously known or recognized.

This definition could include an unanticipated adverse device effect, any serious adverse effect on health or safety or any life-threatening problem or death caused by, or associated with, a device, if that effect, problem, or death was not previously identified in nature, severity, or degree of incidence in the investigational plan, or any other unanticipated serious problem associated with a device that relates to the rights, safety, or welfare of subjects (21 CFR 812.3(s)).

PRIVACY AND CONFIDENTIALITY

REGULATORY, ETHICAL, AND STUDY OVERSIGHT CONSIDERATIONS

Informed Consent Process

An informed consent form (in written paper or in electronic format) describing in detail the study intervention, study procedures, and risks is given to each subject and written or electronically captured with identity verification documentation of informed consent is required prior to the subject starting any study activities, including study qualification evaluation. There are no other consent documents provided to subjects in this study.

Informed consent is a process that is initiated prior to the individual’s agreeing to participate in the study and continues throughout the individual’s study participation. Consent forms will be IRB-approved, and the subject will be asked to read and review the document. The investigator will explain the research study to the subject and answer any questions that may arise. A verbal explanation will be provided in terms suited to the subject’s comprehension of the purposes, procedures, and potential risks of the study and of their rights as research subjects. Subjects will have the opportunity to carefully review the written consent form and ask questions prior to signing. The subjects will have the opportunity to take the consent form home, and to discuss the study with their family or surrogates or think about it prior to agreeing to participate. The subject will sign the informed consent document prior to any procedures or activities being done specifically for the study. Subjects will be informed that participation is voluntary and that they may withdraw from the study at any time, without prejudice. A copy of the informed consent

document will be given to the subject for their records. The informed consent process will be conducted and documented in the source document (including the date), and the form signed by both the subject and the site staff member who reviewed the consent form with the subject before the subject undergoes any study-specific procedures or activities. The rights and welfare of the subjects will be protected by emphasizing to them that the quality of their medical care will not be adversely affected if they decline to participate in this study.

- Informed consent will be an agreement between the individual investigator and each subject, having the capacity to understand and make an informed decision. Consent will be obtained prior to each potential subject's participation in this clinical study.
- Each subject participating in this clinical study will be made aware of the fact that his or her participation involves research and the intent of the research, the expected duration of his or her participation and a description of the procedures that will be followed.
- Each subject will be made aware of the reasonably expected benefits he or she might receive, as well as any risks or potential discomfort that are involved.
- Each subject will also be made aware of alternative treatments available to him or her.
- Each subject will be made aware that his or her records will remain confidential, but that the FDA and the IRB has the right to inspect his or her records.
- Each subject will be told that his or her participation in the clinical study is voluntary, without force or influence from the investigator or sponsor.
- Each subject will be given the name and method of contacting the appropriate person(s) to answer his or her questions about the research and in the event of a research-related injury.

The informed consent form that will be used to collect the data from each subject in this clinical study can be found in **Appendix B**.

Confidentiality and Privacy

Subject confidentiality and privacy are strictly held in trust by the participating investigators, study staff, and the sponsor(s) and their interventions. Therefore, the study protocol, documentation, data, and all other information generated will be held in strict confidence. No information concerning the study, or the data, will be released to any unauthorized third party without prior written approval of the sponsor.

All research activities will be conducted in as private a setting as possible.

The study monitor, other authorized representatives of the sponsor, representatives of the IRB, or regulatory agencies may inspect all documents and records required to be maintained by the investigator for the subjects in this study. The clinical study site will permit access to such records.

Records for each subject in this clinical study will be maintained in separate files in a locked filing cabinet at the test site. The investigator at the test site will be responsible for ensuring that all records for a subject pertaining to his or her participation in the clinical study are always stored in that subject's file other than when information is being recorded on them.

The study Monitor will have access to the files for the purposes of data monitoring and auditing. Once the study is complete, copies of each of the subject case report forms will be made and supplied to the study statistician for analysis of results. The study statistician will maintain these copies in a separate clinical study file that is kept in a locked filing cabinet on their premises.

The original records will be maintained at the respective test sites upon completion of the study in their original files and stored in a locked filing cabinet.

Subjects' identities will be kept confidential by assigning each subject a unique de-identified subject ID upon acceptance into the study as explained above. Paper consent forms containing subject names and signatures will be maintained in separate folders stored in a separate locked location from the subject binders such that no association between a subject's name and his or her Subject ID can be formed.

At the end of the study, all records will continue to be kept in a secure location for as long a period as dictated by the FDA, reviewing IRB, Institutional policies, or sponsor requirements.

A description of this clinical trial will be available on <http://www.ClinicalTrials.gov>, as required by U.S. Law. This web site will not include any identifiable information for subjects. At most, the web site will include a summary of the study results.

QUALITY ASSURANCE AND STUDY MONITORING

STUDY DATA MONITORING

The study sponsor will be responsible for monitoring the study sites to review the data being collected. The sponsor shall implement and maintain quality control and quality assurance procedures with written standard operating procedures (SOPs) to ensure that the trial is being conducted and data are generated, documented, and reported in compliance with the protocol, Good Clinical Practice (GCP) and applicable regulatory requirements.

The investigator agrees to allow the monitor and other authorized personnel direct access to source data/documents for trial related monitoring, the clinical supplies storage/dispensing area and to provide all documents in the Investigator Regulatory File (or Site Regulatory Binder) for review, and to assist site auditors in their activities if requested. Requests by the FDA to inspect the study site may be made after adequate notification. The investigator may be required to assist the regulatory inspectors in their duties, if requested.

A Clinical Trial Monitoring Plan will be in place to ensure on-going compliance and accuracy of procedures throughout the trial.

QUALITY ASSURANCE AND QUALITY CONTROL

The clinical site will perform internal quality management of study conduct, and data collection, documentation, and completion per the site's SOP and quality management plan.

Quality control (QC) procedures will be implemented beginning with data entry and data QC checks that will be performed on the recorded data. Any missing data or data anomalies will be communicated to the site(s) for clarification/resolution.

Following written Standard Operating Procedures (SOPs), the monitors will verify that the clinical trial is conducted, and data are generated, and documented (recorded) in compliance with the protocol, ICH GCP, and any other applicable regulatory requirements.

The investigational site will provide direct access to all trial related sites, source data/documents, and reports for the purpose of monitoring and auditing by the sponsor, and inspection by local and regulatory authorities.

DATA HANDLING AND RECORD KEEPING

Data Collection, Recording and Management Responsibilities

Study documents pertaining to data collection will be developed by the sponsor to record all study data and assure compliance to the protocol. All data collection documents will be tracked and monitored for completion and accuracy by sponsor-assigned monitor(s).

Data collection is the responsibility of the clinical trial staff at the site under the supervision of the site investigator. The investigator is responsible for ensuring the accuracy, completeness, legibility, and timeliness of the data reported. All source documents should be completed in a neat, legible manner to ensure accurate interpretation of data.

Case Report Forms

The case report forms that will be used to collect the data from each subject in this clinical trial can be found in **Appendix C**.

Data Confidentiality

All physical copies of subject medical records, source and other research documents will be stored in secure cabinets at the study site. All such study documentation containing subject information will be identified by the de-identified coded subject ID only. There will be no identifying information included on any subject CRFs or other source documentation, per HIPAA. Subject confidentiality will be protected to the greatest extent possible.

Study Records Retention

The investigator is responsible for retaining a copy of all study records for three (3) years after the study is completed or terminated. All original study data will be retained by the sponsor for no longer than five (5) years after the study is completed or terminated.

PROTOCOL DEVIATIONS

A protocol deviation is any noncompliance with the clinical trial protocol, ICH GCP, or Manual of Procedures (MOP) requirements. The noncompliance may be either on the part of the subject, the investigator, or the study site staff. As a result of deviations, corrective actions are to be developed by the site and implemented promptly.

These practices are consistent with ICH GCP:

- 4.5 Compliance with Protocol, sections 4.5.1, 4.5.2, and 4.5.3
- 5.1 Quality Assurance and Quality Control, section 5.1.1
- 5.20 Noncompliance, sections 5.20.1, and 5.20.2.

It is the responsibility of the site investigator to use continuous vigilance to identify and report deviations within 5 working days of identification of the protocol deviation, or within 5 working

days of the scheduled protocol-required activity. All deviations must be addressed in study source documents (CRFs) and be reported to the sponsor. Protocol deviations must be sent to the reviewing IRB as applicable per their policies. The site investigator is responsible for knowing and adhering to the reviewing IRB requirements.

The investigator will not intentionally deviate from the study protocol procedures except in medical emergencies. Any and all protocol deviations that do occur will be recorded on the CRF and the IRB will be informed of the deviation, if applicable.

Protocol deviations will be recorded in CRFs and monitored for completion and accuracy during each monitoring visit.

SUBJECT SAFETY MONITORING

Subject safety data will be recorded in CRFs and monitored for completion and accuracy during each monitoring visit.

Subjects will be asked about any adverse events at the test site and are required to record any potential adverse events in the Adverse Events Record Form and to notify the test site immediately. In such an occurrence, an unscheduled visit may be arranged so that the Investigator can clinically evaluate the findings. All adverse events will be recorded and reported as per the plan described in the relevant section above.

The Investigator can decide to stop the subject's participation in the study if he/she believes that subjects' participation is no longer safe.

The sponsor or the IRB may stop the research for the safety of the subjects if unreasonable risks to subjects persist.

PROTOCOL AMENDMENTS

Any amendments required to the clinical study protocol will be submitted for approval to the IRB before implementation. Subjects will be re-consented for these amendments as applicable.

END OF DOCUMENT

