Mobility in the neck/shoulder region will be measured using a universal inclinometer, as follows:

- (i) Shoulder ROM will be measured from a seated passive abduction, the relaxed position of parallel to the side of the body through full extension above the head. Maximum movement is 180 degrees.
- (ii) Neck ROM will be measured in a supine position, from forward position to face over shoulder. Maximum movement is 90 degrees.

SUBJECT SATISFACTION WITH STUDY OUTCOME

The subject is asked to rate how satisfied he or she is with any change in neck/shoulder pain following completion of the laser administration procedure with the Erchonia Lasers by using the 5-point Likert scale below to respond to the following question: "Overall, how satisfied or dissatisfied are you with any change in the pain in your neck and/or shoulder following the study treatment with the study laser devices?"

- Very Satisfied
- Somewhat Satisfied
- Neither Satisfied nor Dissatisfied
- Not Very Satisfied
- Not at All Satisfied

STUDY PROCEDURE PROTOCOL

PRE-TREATMENT ACTIVITIES

Pre-treatment activities will be performed at the study site prior to administering the sequential Erchonia® PPL blue laser therapy followed by the standard Erchonia XLR8 red laser therapy.

STUDY QUALIFICATION

SIGNING OF INFORMED CONSENT FORM

The PI will commence by presenting and reviewing in detail the items in the informed consent form with the individual and answer any questions. To proceed, the individual must willingly sign the informed consent form.

ASSIGNMENT OF SUBJECT IDENTIFICATION NUMBER

The subject is assigned a unique de-identified subject identification number based upon his or her order of entry into the study. The Subject ID number will comprise the initials of the test site Principal Investigator's first and last name followed by a single digit number that represents the test site number (e.g. test site #1 = 0, test site #2 = 1, etc.) and then a two-digit number that represents the subject's order of entry in the study.

For example, the 14th subject to be enrolled at test site #2 with Principal Investigator John Black will have a Subject ID of JB114.

STUDY QUALIFICATION EVALUATION: INCLUSION/EXCLUSION CRITERIA

INCLUSION CRITERIA

To be eligible for study participation, a subject must satisfy each of the following criteria.

1. Signed informed consent form
2. 22 years of age or older
3. Primary language is English
4. Subject presents with one or more of:

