24 HOURS AND 48 HOURS POST-TREATMENT EVALUATIONS

The subject will be required to record the following at home on the forms provided by the test site at 24 hours and again at 48 hours after completion of the treatment administration phase at the test site.

OUTCOME ASSESSMENTS

- Visual Analog Scale (VAS) Degree of Pain Rating
- Linear Range of Motion (ROM)
- Subject Satisfaction with Study Outcome Rating
- Adverse Events Evaluation

STATISTICAL ANALYSIS PLAN

Populations Examined

Two (2) subject populations will be analyzed, as applicable:

- (i) **Intent-to-Treat (ITT) Population:** All enrolled subjects regardless of whether any measures are recorded and/or treatment is administered.
- (ii) **Per-Protocol (PP) Population:** All enrolled subjects who completed the study per protocol through to the 48-hour post-treatment evaluation, excluding subjects with major protocol deviations, incompletes, etc.

Primary analysis of efficacy will be according to the intent to treat (ITT) population and the secondary supportive analysis will be according to the per protocol (PP) population. Non-inferiority will be established if both the ITT and PP analyses agree.

Handling of Missing Data

Missing data will be handled through multiple imputation analysis, a strategy to handle missing values in a clinical trial wherein each missing value is replaced with a set of plausible values that represent the uncertainty about the right value to impute. The exact method of multiple imputation analysis will be determined after study completion depending on factors such as the amount of missing data and whether it is determined that the data are missing at random (MAR) or missing not at random (MNAR).

PRIMARY EFFICACY OUTCOME MEASURE: CHANGE IN SUBJECT SELF-REPORTED VAS PAIN RATING FROM BASELINE TO STUDY ENDPOINT

The aim of this study is to determine if the treatment effect of the sequential therapy with the Erchonia® PPL blue laser therapy followed by the Erchonia® XLR8 standard red laser therapy for the active treatment group in this study is equal to or superior to that attained for the active comparative treatment group in the comparative reference study who received the standard red laser therapy alone.

Proportion of Successes

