The primary efficacy outcome measure for this clinical study is identical to that of the comparative reference study and is defined as the change in subject self-reported Visual Analog Scale (VAS) pain rating from baseline to study endpoint evaluation, with study endpoint defined as within 3 minutes of completion of the study single sequential treatment administration with the Erchonia® PPL blue laser therapy followed by the standard Erchonia red laser therapy administered using the Erchonia® XLR8.

Individual Subject Success Criteria

individual subject success criteria is defined as a 30% or greater decrease in self-reported neck and shoulder pain rating on the 0-100 VAS at study endpoint relative to baseline.

Overall Study Success Criteria.

Overall study success criteria is defined as at least 65%±5% of subjects in the current study meeting the study individual subject success criteria.

Justification for Study Success Criteria

The clinical relevance and justification of the individual and overall study success criteria is as follows:

- This study is a non-inferiority study, such that the research hypothesis is that the sequential combination therapy with the Erchonia® PPL blue laser and the standard Erchonia red laser therapy is either equivalent to or superior to the standard Erchonia red diode only therapy in effecting a clinically meaningful reduction in neck and shoulder pain of musculoskeletal origin, based upon the data attained from the red diode only clinical trial conducted in 2001 whose results successfully supported 510(k) clearance of application of the PL3000 red diode only for the identical indication being sought through the results of this clinical trial.
- The individual subject success criteria in this clinical study is identical to that of the comparative reference study.
- The overall study success criteria in this clinical study is based on the actual proportion of individual subject successes attained during the comparative reference trial for the active red diode treatment group, of 65%. The $\pm 5\%$ is the selected equivalence margin (δ), the maximally clinically acceptable difference for which the range of values (60% to 70%) for which the efficacies are “close enough” to be considered equivalent.
- Non-inferiority will be established if the proportion of subjects who attain the individual subject success criteria is no more than 5% less than the reference subject group (i.e. no less than 60%).

Hypotheses

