- Change in mean neck and shoulder pain VAS ratings across study duration: baseline, endpoint, 24 hours, and 48 hours post-procedure.
- Change in linear ROM measurements at study endpoint relative to baseline.
- Subject satisfaction with study outcome ratings across study duration.

INDIVIDUAL TEST SITES

Results will be presented by individual test site for comparison.

INDIVIDUAL SUBJECT RESULTS

Individual subject results for the primary study outcome measure will also be presented.

SAFETY ANALYSIS

Safety analysis will be based on all enrolled subjects and will be assessed by evaluating and comparing the frequency and incidence of observed and/or reported adverse events between subjects enrolled in the current study and subjects enrolled in the comparative reference study. A chi-square test with a continuity correction will be performed to compare the percentage of subjects who had adverse events between the two subject groups.

ADVERSE EVENTS

At each evaluation and measurement point throughout the clinical study, and at any other time throughout the duration of the clinical trial that is necessary, all potential adverse events reported by a subject or observed by an investigator will be recorded on the case report form, and subsequently evaluated by the investigator for its relation to the study procedure and whether any corrective action needs to be taken. All potential adverse events recorded will be appropriately reported to the governing IRB, as applicable.

It is unlikely and not expected that any adverse events will result from implementation of this clinical study protocol. Prior clinical trials evaluating application of Erchonia low level laser light, including numerous evaluating Erchonia lasers for the treatment of various pain conditions, including neck and shoulder nociceptive pain of musculoskeletal origin, have not typically yielded any adverse events or reactions.

ADVERSE EVENTS DEFINITION

An adverse event means any untoward medical occurrence associated with the use of an intervention in humans, whether or not considered intervention-related (21 CFR 312.32 (a)).

SERIOUS ADVERSE EVENTS (SAE) DEFINITION

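### Per-protocol membership runs to 48 hours but the primary outcome is taken within 3 minutes of treatment, so a missed home evaluation can remove a valid primary outcome from an analysis that non-inferiority requires

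*Combined protocol and SAP*

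**What the plan says.** Under Populations Examined in the Statistical Analysis Plan, ITT is "All enrolled subjects regardless of whether any measures are recorded and/or treatment is administered" and PP is "All enrolled subjects who completed the study per protocol through to the 48-hour post-treatment evaluation, excluding subjects with major protocol deviations". The PP definition leaves out incomplete cases too. The section calls ITT primary and PP secondary and supportive, then adds: "Non-inferiority will be established if both the ITT and PP analyses agree".

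The primary efficacy section measures VAS change from baseline to study endpoint, "with study endpoint defined as within 3 minutes of completion of the study single sequential treatment administration". The treatment-phase evaluations and the Evaluation Time Point paragraph give the same timing.

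The later data come from the subject. The section on the 24- and 48-hour evaluations states: "The subject will be required to record the following at home on the forms provided by the test site at 24 hours". The same recording is required a day later. The list of items includes linear range of motion (ROM). The ROM section specifies a universal inclinometer: "Shoulder ROM will be measured from a seated passive abduction", with the neck measured supine. The only ROM analysis under Secondary Evaluations is "Change in linear ROM measurements at study endpoint relative to baseline".

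**The concern.** Everything needed to classify a subject as responder or non-responder is known minutes after treatment. PP membership is settled up to two days later, by whether the subject completed a home evaluation. A subject can have the full PPL and XLR8 session and a valid baseline and 3-minute VAS, and still leave PP for a reason unrelated to the validity of that outcome.

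This matters because PP carries weight in the decision, despite its supportive label. Selection also happens after the outcome. If returning the forms is related to relief, the PP responder rate is biased, in a direction that cannot be known in advance. The multiple imputation described under Handling of Missing Data does not help: the primary value is not missing, and the subject is excluded by definition.

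Home ROM adds to the risk. The method calls for an inclinometer and, for the shoulder, passive movement. The documents describe no home instrument or assistant, and no listed analysis uses the 24- or 48-hour ROM values. The item is nevertheless part of the evaluation that PP membership depends on.

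**Working it through.** **Inputs from the documents.** Sample size 43 (Sample Size), set equal to the reference active arm. Reference responder rate 65.1% (supporting clinical data). Margin 5 points, threshold 60% (Justification for Study Success Criteria; Hypotheses). The plan names no test or confidence interval for the proportion, so the main check uses the rule that the observed rate exceeds 60%.

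**The plan's own figures.** 28/43 = 65.1%, which matches the reference rate. 65% − 5% = 60%, which matches the null hypothesis.

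**Threshold count.** 0.60 × 43 = 25.8, so ITT needs 26 responders. One subject is 1/43 = 2.3 points.

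**How many lost responders make PP fail.** With x responders in ITT and k responders (no non-responders) lacking 48-hour completion, the PP rate is (x − k)/(43 − k).

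| ITT | Smallest k for PP to fail | PP |
|---|---|---|
| 26/43 = 60.5% | 1 | 25/42 = 59.5% |
| 27/43 = 62.8% | 3 | 24/40 = 60.0% |
| 28/43 = 65.1% | 6 | 22/37 = 59.5% |

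The middle row fails the hypothesis as written (above 60%), but would pass the justification text, which accepts 60% itself.

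**The other direction.** 25/43 = 58.1% fails ITT. If two non-responders are incomplete, PP is 25/41 = 61.0%. PP then looks better than the full data, although ITT still blocks success.

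**Chance that both sets pass.** Let X ~ Bin(43, p) be the responders, A ~ Bin(X, 1 − d_R) the responders kept in PP, and B ~ Bin(43 − X, 1 − d_N) the non-responders kept. ITT passes if X/43 > 0.60, and PP passes if A/(A + B) > 0.60. The joint probability is summed exactly over X, A and B. ITT is taken to use the observed 3-minute outcome for all 43. The non-return rates d_R and d_N are assumptions. At p = 28/43:

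| d_R | d_N | ITT passes | PP passes | Both pass |
|---|---|---|---|---|
| 0 | 0 | 0.790 | 0.790 | 0.790 |
| 5% | 5% | 0.790 | 0.743 | 0.735 |
| 10% | 10% | 0.790 | 0.738 | 0.721 |
| 20% | 20% | 0.790 | 0.726 | 0.696 |
| 20% | 5% | 0.790 | 0.547 | 0.546 |
| 5% | 20% | 0.790 | 0.875 | 0.783 |

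The first row is what the plan would have if membership were fixed at the 3-minute assessment and there were no other major deviations. The last row shows PP more favourable than ITT (0.875 against 0.790) while the joint chance stays below ITT. At a true rate of exactly 60% with the same 5%/20% pattern, PP passes with probability 0.690 against 0.541 for ITT, and both pass with probability 0.533.

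**Sensitivity to the rule.** Under an assumed exact one-sided 0.025 test against 60%, 33/43 are needed. The joint chance at 65.1% is 0.072 with full completion, 0.060, 0.052 and 0.043 at 5%, 10% and 20% random non-return, and 0.021 with 20% of responders against 5% of non-responders lost.

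**The case against.** The strongest reply is that requiring PP in addition to ITT can only lower the chance of declaring success. That stands. A reader might infer from 25/43 becoming 25/41 that drop-out could produce a false non-inferiority claim. It cannot, because ITT has already failed. What remains is that PP can move the wrong way for a check.

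The reply can add that one lost responder is the threshold case, and that at the reference result six must be lost with no non-responder lost. That also stands, as does the fact that every non-return rate here is assumed.

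Some stronger readings are tempting but not supported:

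- **That nobody can complete the 48-hour evaluation, because home ROM is impossible alone.** The plan does not define what makes a subject incomplete or say that one blank item excludes. Subjects are to be instructed on the forms, and the forms are not in the text available. Passive movement is specified for the shoulder only. Feasibility is a fair question; impossibility is not shown.
- **That taking analgesics within 48 hours removes a subject from PP.** Inclusion criteria 8 and 9 concern willingness and ability to refrain. No text lists such use as a major deviation, and that term is undefined.
- **That two failing analyses would establish non-inferiority because they agree.** The success criterion is stated elsewhere, so this is loose wording, not a real loophole.
- **That restricting the secondary summaries to PP is an error.** They are descriptive and support no claims, so this is a matter of preference.

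**Conclusion.** The concern holds as a mismatch of windows. Missing the 48-hour evaluation excludes a subject from PP, the primary outcome is complete at 3 minutes, and PP must support the conclusion. The plan is also inconsistent about whether PP is supportive or required.

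The effect on the decision is conservative. At a true rate of 65.1% the joint chance of success falls by 0.055 to 0.094 under 5% to 20% random non-return, and by 0.244 if 20% of responders but 5% of non-responders are lost. These sizes rest on the assumed rates, on independent losses within each response group, and on the point-estimate rule. The mismatch itself rests on none of them. Whether a blank home ROM entry alone excludes a subject is left open. The study is open-label, so that choice could be made after the 3-minute result is known.

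**What to change.** 1. Define PP for the primary endpoint as: eligible, full PPL plus XLR8 session received, baseline and 3-minute VAS recorded, and no major deviation up to the 3-minute assessment. State in advance what counts as a major deviation.
2. Use a separate 48-hour completer set only for the 24- and 48-hour summaries.
3. Do not let PP membership depend on home ROM. Drop the item, or confirm that it is feasible at home.
4. Replace the agreement sentence with a statement that ITT and PP must each meet the non-inferiority criterion, and reconcile this with the supportive label.

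The cost is protocol and SAP wording, plus the possible loss of 24- and 48-hour ROM, which no planned analysis uses. No subjects or visits are added.
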